Sample Size and Power Estimates. A provider group within the proposed study setting reported a 29.4% prevalence of GBS positive women among the 316 who gave birth in 2016. Therefore, we expect a 30% GBS prevalence in the placebo group compared to the probiotic group. To determine the effect size of the intervention, a sample of 80 women will be required to test the difference in proportions of GBS colonization and IAP between groups (hypotheses 1a and 1d). Hypotheses are unidirectional. With the sample size of 80 and setting alpha = 5%, one tailed test, 80% power estimate, and confounding variables (yogurt ingestion, vaginal cleansing practices, and sexual activity) accounting for multiple R-square = 0.1, we will be able to reject the null hypothesis for an effect size of Odds Ratio (OR) = 0.17 for the logistic regression to compare the proportion of GBS positives between groups. When comparing the colony counts (GBS and Lactobacillus) and GI symptoms (hypotheses 1b, 1c and 2), the same sample size = 80, power = 80%, alpha = 5%, one tailed test; we can reject the null hypothesis for a Cohen d = 0.56. This is a medium effect size, indicating that we can detect a difference between groups equivalent to 0.56 standard deviations. However, if the effect of the treatment is smaller we will be able to identify it, but not reject the null hypothesis of being equal to 0. This information is important for design of a full scale efficacy trial of the probiotic intervention. In our published preliminary study, 15 we found an overall dropout rate of 23%, but 30% in the probiotic group. For the proposed study, we chose a conservative 30% dropout rate to assure that the sample size can be fully achieved within the study timeline. Therefore, a total sample of 116 will be targeted for enrollment. Hypotheses 1b, 1c, and 2 will be tested by doing a multiple group comparison of the change in colony count for GBS and Lactobacillus, and the GI symptom inventory (M-SODA-9) scores [Section 2.3.1.8.e].

Recruitment. A sample of 116 women who meet the inclusion criteria, low-risk, healthy and pregnant, 26 ± 2 weeks gestation, 18 years of age, will be recruited from a population of central city maternity care recipients who see either certified nurse-midwives or physicians at the prenatal clinics of Aurora Sinai Medical Center (ASMC) in Milwaukee, Wisconsin. Approximately 200 new prenatal patients are seen monthly. **Inclusion and exclusion criteria are detailed in Table 1.**

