numbers, in an encrypted computer file, accessible only to the PI and the SC. The PI, co-investigators, SC, prenatal providers, and participants will be blind to group assignment. Data will be collected at five time points: T1 baseline (28 ± 2 weeks), T2 (36 ± 2 weeks), T3 (1-2 days post birth, before hospital discharge), T4 (2 weeks post birth phone call), and T5 (2 months post birth follow-up phone call). Measures and documentation tools appear in Appendices A through G. At each study visit, participants will be asked about any potential adverse events. Immediately following IC, participants will have their first study visit at 28 ± 2 weeks gestation (T1), during which baseline data will be collected and they will receive instructions to take one capsule by mouth daily until the time of birth. Also at T1 (28 ± 2 weeks), the participant will be seen by her prenatal provider, who will facilitate collection of the baseline study samples. Participants will be asked to collect their own vaginal and rectal swabs with assistance, but have the option of provider collection. This minimally invasive testing does not require a speculum exam. Self-collected swabs yield similar colonization measures compared to provider-collected, but may be more acceptable to women. 63,64 Each participant will also complete three brief questionnaires at T1. Vaginal and rectal swabs and 2 questionnaires will be collected at T2 (36 ± 2 weeks). At the end of T2, participants will receive a \$25 gift card. At T3, the SC will visit every participant on the postpartum hospital unit to administer two brief questionnaires, retrieve the study bottle with MEMS cap, and give a \$75 gift card. The SC will analyze the MEMS cap data, count and record the capsules remaining in the bottle, and conduct a chart review. At T4 and T5, the SC will text message the participants to indicate that she/he will be phoning the next business day. The following day, a phone call will be made to the participant to elicit any maternal and child health events (e.g., illness, antibiotics, or hospital readmission). At T5, the SC will also retrieve health records for the participant and her infant to examine them for the same maternal or child health events.

Table 2. Summary of Study Data Collection, Variables, Measures, and Timing

Outcome Variables	Study Data Collection	T1	T2	T3	T4	T5
	SC will document data from all measures on the Summary	28 ± 2	36 ± 2	1-2 days	2	2

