Plan for Missing Data. To estimate the overall treatment effect for the entire sample, an "intention to treat" analysis will be conducted, using our above likelihood-based analysis method for repeated measures, including data on all subjects who were randomized to study groups, thus allowing us to use all available data, rather than delete participants with missing values from the analysis of treatment effects. ^{67,68} Pattern mixture modeling ⁶⁹ will be used to understand the effects of protocol compliance. Thus, treatment effectiveness during the full intended duration of the protocol can be compared with the effectiveness of treatments while participants are compliant with them. ⁷⁰

Binary Outcomes Analyses: Aim 1. Using an intention-to treat approach, subjects will not be dropped from any preliminary analysis due to varying degrees of adherence with their group-specific therapy. The main hypothesis, 1a, along with hypothesis 1d, assess differences in proportions, and will be analyzed using a generalized linear model (GLM).^{71,72} Those response variables that are dichotomous (binomial distribution) will be analyzed using the logit link to assess the proportional difference in GBS-colonized women (hypothesis 1a)

and the proportion of women requiring IAP (hypotheses 1d). GLM allows us to include confounding variables in the same model providing an effect size measure for the treatment and confounding variables, the odds ratio (OR), which has direct interpretation as the odds difference of testing GBS positive.

Continuous Outcomes Analyses: Aims 1 and 2. A secondary analysis of research aims 1 and 2 will be conducted using a Gaussian distribution-based multilevel generalized linear mixed model to assess group differences in GBS (hypothesis 1 b) and *Lactobacillus* (hypothesis 1c) colony count changes from 28 weeks to 35-37 weeks, ⁷³ with time points (T1-T2) nested within subjects. Group differences can be estimated for both initial time point and slope. The treatment is expected to show a meaningful difference to the slope of colony count change. Confounding variables will be included as time-invariant covariates. Parameters that appear to be meaningless will be excluded, using log-likelihood (deviance) model comparison with a direct interpretation as the colony count slope difference between groups, which can be transformed into a standardized difference (Cohen's *d*).

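### For the secondary colony-count hypotheses (1b, 1c), a baseline-constrained model with a protected group-by-time term would usually gain precision at almost no cost and would remove an unspecified parameter-exclusion step

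*Combined protocol and SAP*

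**What the plan says.** Under Continuous Outcomes Analyses: Aims 1 and 2, GBS and Lactobacillus counts are analysed with a Gaussian mixed model, with T1 and T2 as repeated outcomes within each woman. On the arm effects, the section states: "Group differences can be estimated for both initial time point and slope".

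On model reduction it says: "Parameters that appear to be meaningless will be excluded, using log-likelihood (deviance) model comparison with a direct interpretation as the colony count slope difference". The arm contrast in slopes is thus the quantity to be read from the model, and it may be re-expressed as Cohen's d.

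On adjustment, the section says: "Confounding variables will be included as time-invariant covariates". The confounders named under Sample Size and Power Estimates are yogurt, vaginal cleansing and sexual activity. The T1 count is not listed as a covariate anywhere.

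Procedure and Timing makes T1 the pre-treatment visit. It is the visit at which "baseline data will be collected and they will receive instructions to take one capsule by mouth daily until the time of birth", and the prenatal provider is the one "who will facilitate collection of the baseline study samples". Items b and c after Table 2 confirm that both organisms are counted at T1 and T2.

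Sample Size and Power Estimates says 1b and 1c are "tested by doing a multiple group comparison of the change in colony count for GBS and Lactobacillus", with "the same sample size = 80, power = 80%, alpha = 5%, one tailed test" and a detectable d of 0.56. It adds that smaller effects will still be identified: "This information is important for design of a full scale efficacy trial of the probiotic intervention". Plan for Missing Data commits to a likelihood analysis of all randomized women using all available data.

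**The concern.** Two features of the model deserve attention.

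**Free T1 difference.** In a randomized trial the arms have the same expected count before treatment. Estimating an arm difference at T1 uses information on a quantity known to be zero in expectation. The T1 counts are already collected and could instead reduce the error variance of the treatment contrast.

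**Open-ended exclusion.** Parameters may be removed by deviance comparison, but no cut-off is given and no term is named as always kept. The error rate and power for 1b and 1c then depend on a choice made after seeing the data.

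The stake is precision and a well-defined test for secondary outcomes whose estimates are meant to inform a larger trial. Validity of the planned contrast is not at issue.

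**Working it through.** **1. The plan's own figure.** Inputs from Sample Size and Power Estimates: 80 evaluable women, one-sided 5%, d = 0.56. The 58 + 58 bottles imply 1:1 allocation, so 40 per arm.

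Power = Φ(0.56 × √(40/2) − 1.645) = Φ(2.504 − 1.645) = Φ(0.859) = 0.805; the noncentral t gives 0.799. Enrolment: 40/0.7 = 57.1, so 58 per arm and 116 in total. Both stated figures reproduce.

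**2. Variance of the two contrasts.** Assumed, because the documents give neither: rho, the T1-T2 correlation, and k = SD(T1)/SD(T2). Per woman, in units of the T2 variance:

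- change score (the planned slope, complete pairs): k² + 1 − 2·rho·k
- baseline-constrained or baseline-adjusted: 1 − rho²
- ratio: 1 + (k − rho)²/(1 − rho²)

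For k = 1 and rho = 0.3: 1 + 0.49/0.91 = 1.54.

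With 58 women per arm at T1 and 40 at T2 (dropout at random assumed), the planned likelihood analysis also uses the unpaired T1 counts. The ratio becomes 1 + (40/58)(k − rho)²/(1 − rho²).

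| k | Ratio, complete pairs, rho 0.3/0.5/0.7 | Ratio, 116 at T1 and 80 at T2 |
|---|---|---|
| 0.7 | 1.18 / 1.05 / 1.00 | 1.12 / 1.04 / 1.00 |
| 1 | 1.54 / 1.33 / 1.18 | 1.37 / 1.23 / 1.12 |
| 1.25 | 1.99 / 1.75 / 1.59 | 1.68 / 1.52 / 1.41 |

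There is no gain when k = rho. In 60,000 simulated trials with 40 per arm, that worst case cost about 1.5% of variance.

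**3. Power.** Take d = 0.56 in change-score SDs, complete pairs, k = 1. The constrained model gives Φ(2.504 × √ratio − 1.645). For rho = 0.3 this is Φ(2.504 × 1.240 − 1.645) = Φ(1.461) = 0.93. At rho 0.3/0.5/0.7 it is 93/89/86%, against 80% planned. At k = 0.7 it is 86/82/80%.

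**4. Exclusion reaching only the T1 arm term.** Assumed cut-off 3.84, k = 1, known variance, 2 million simulated trials: one-sided alpha is 5.7/5.5/5.3% and power 91/88/85% at rho 0.3/0.5/0.7. Alpha rises because the unadjusted contrast is used exactly when the arms happen to differ at T1.

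**5. Exclusion reaching the slope term.** A deviance comparison on one degree of freedom is two-sided, and 1.645² = 2.71. If the term must first survive a cut-off c, the effective critical value is max(1.645, √c).

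- c up to 2.71: alpha 5.0%, power 80%
- c = 3.84: alpha 2.5%, power Φ(2.504 − 1.960) = 71%
- c = ln 80 = 4.38: alpha 1.8%, power Φ(2.504 − 2.093) = 66%

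In 8,000 simulated trials per setting (rho = 0.5, k = 1, cut-off 3.84), a true effect of 0.30 SD was kept in 27% of trials and averaged 0.56 SD when kept. A true effect of 0.56 SD was kept in 70% and averaged 0.67 SD.

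**The case against.** The strongest reply is that the plan already uses T1, because its outcome is change from T1 and that contrast is unbiased under randomization. Adjusting for the T1 count is then an efficiency preference, and its size rests wholly on rho and k, which the documents do not give. The sentence on the initial time point is permissive: it says the difference can be estimated, not that it must stay in the model. The natural target of the exclusion rule is a null T1 arm term, and dropping that term recovers most of the gain (91/88/85% power against 93/89/86%). The outcomes are secondary.

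Most of this stands. A reader might infer that the plan ignores baseline or yields a biased effect; it does neither. A reader might also infer that the treatment term will be excluded. The rule does not rule this out, but the same sentence goes on to interpret the slope difference and convert it to Cohen's d, which presupposes that the term is kept. The figures in step 5 therefore show why a stated exemption is worth having; they do not describe what the plan intends.

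What the reply leaves open is that the gain comes back only through a data-driven step with no stated cut-off and a slightly raised alpha. Prespecifying the constraint gives the same benefit without that step.

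**Conclusion.** This is a near-free improvement to a secondary analysis, not an error in it. The planned contrast is valid. With equal SDs its variance is 1.18 to 1.54 times that of the baseline-constrained model in complete pairs, and 1.12 to 1.37 times with 116 women at T1 and 80 at T2, for assumed rho from 0.7 down to 0.3. The gain is larger if T1 is more variable than T2 and nil if k = rho. The figures assume Gaussian outcomes. The exclusion rule adds roughly 0.3 to 0.7 percentage points to alpha on the natural reading (k = 1, assumed cut-off 3.84).

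A reader might infer that the trial is underpowered for 1b and 1c. The documents do not support that. The stated power reproduces when d = 0.56 is read in change-score SDs, which fits hypotheses framed as change. Only if d were in T2 SDs would the planned slope fall short, and then only at lower correlations (68% at rho = 0.3, 80% at 0.5, k = 1); the text does not say that d is on that scale.

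**What to change.** Before unblinding, amend Continuous Outcomes Analyses as follows.

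1. For each colony-count outcome, prespecify a longitudinal model with a common T1 mean across arms and an unstructured 2×2 covariance, including all randomized women with any count.
2. Always retain group-by-time, test it one-sided at 5% as in Sample Size and Power Estimates, and report its estimate and confidence interval whatever the result.
3. Delete the parameter-exclusion sentence. The constrained model alone does not protect the treatment term, so items 2 and 3 are both needed.
4. Use ANCOVA of T2 on T1 only as a sensitivity analysis. It drops women without a T2 count, contrary to the commitment in Plan for Missing Data.

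The cost is SAP wording: no new data, visits or patients, and at worst about 1.5% of variance with 40 per arm. The sample size of 80 evaluable and 116 enrolled stays as it is. If allocation is already known to the analysts, the constrained model should be labelled as a post hoc sensitivity analysis.

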- g.2. Participants will complete the **Questionnaire for Women (Q4W)** at T1-T3 visits. To improve the reliability of subject recall, the Q4W asks for a report of the past week's ingestion of yogurt, vaginal cleansing practices, and sexual activity. The Q4W was used by the co-investigators in our preliminary study.¹⁸
- h. **Maternal-Infant Postpartum Health Events.** The SC will interview the participant for a history of postpartum health events for herself or the infant (T4 and T5) and document appropriately on two forms:
 - h.1. Maternal health events, recorded on Maternal Peripartal Health Check (MPHC).
 - h.2. Infant health events, recorded on Infant Health and Wellness Form (IHWF).
- i. **Adverse Events.** All providers and study personnel will solicit information about potential adverse events (AE) at each study visit (T2 through T5). Participants will be asked to report any suspected side effects or AE at any point in between study visits to their providers, who will then notify the PI, and follow the protocol established in the Human Subjects Section. AE will be recorded on **Q4W** (T2, T3), **MPHC and IHWF** (T4-T5). **Data Management.** Database and entry screens for this project will be developed using Epidata. To minimize errors, data will be double-entered and checked for invalid codes, values that are out of range, invalid dates, and skip patterns. All data will be verified against the original forms and imported to Epidata for analysis. **Descriptive Analyses.** Means, standard deviations or frequency distributions will be reported for all variables. We will test for differences in demographic characteristics of two groups (Florajen3 and placebo), including confounding variables such as sexual activity, vaginal hygiene practices, yogurt ingestion, and prenatal antibiotic use. Chi-square and independent *t* tests will be used to compare mode of birth, gestational age at birth, and birth weight and length, to assess equivalence of groups. Chi-square, Fischer's exact tests, and Wilcoxon methods will be used to test for difference among binary and categorical variables.

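### Confounders entered only as main effects would do almost nothing for the T1–T2 slope contrast that tests hypotheses 1b and 1c; the plan should specify covariate-by-time terms

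*Combined protocol and SAP*

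**What the plan says.** Under Continuous Outcomes Analyses: Aims 1 and 2, GBS and *Lactobacillus* colony counts are to be analysed with a "Gaussian distribution-based multilevel generalized linear mixed model to assess group differences in GBS" and in *Lactobacillus* counts, "with time points (T1-T2) nested within subjects". On the treatment effect the section states: "Group differences can be estimated for both initial time point and slope", and then: "The treatment is expected to show a meaningful difference to the slope of colony count change". The only instruction about confounders is: "Confounding variables will be included as time-invariant covariates". Nothing is said about whether a covariate acts on the level, on the slope, or on both. A later sentence allows terms to be removed by deviance comparison.

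The confounders are named under Sample Size and Power Estimates, in the calculation for the logistic model: "confounding variables (yogurt ingestion, vaginal cleansing practices, and sexual activity) accounting for multiple R-square = 0.1". Descriptive Analyses adds prenatal antibiotic use to these. Item g.2 describes how the three behaviours are measured: "Participants will complete the Questionnaire for Women (Q4W) at T1-T3 visits", and "the Q4W asks for a report of the past week's ingestion of yogurt, vaginal cleansing practices, and sexual activity". They are therefore collected repeatedly, and the model section does not say which visit's value stands for the woman.

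**The concern.** With two visits per woman, the slope difference between arms is the arm difference in mean change from T1 to T2. A covariate that is constant within a woman and enters as a main effect shifts both of her visits by the same amount, so it drops out of her change. It affects the estimated level but not the contrast on which 1b and 1c are judged.

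The covariate step would then have almost no effect on the test it accompanies. Simple randomization with about 80 evaluable women can leave the arms unequal on yogurt use, cleansing or sexual activity, and Descriptive Analyses plans to look for such differences. If one appeared, and the behaviour predicted change in counts, this model could not respond to it. Any precision available from covariates that predict change would also be forgone.

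**Working it through.** **Inputs.** From Sample Size and Power Estimates: 80 evaluable women, one-tailed alpha 5%, 80% power, d = 0.56, 30% dropout, 116 enrolled, and R-square 0.1 for the logistic model only. From Randomization Procedures: 58 bottles per arm. From the continuous-outcomes section: two time points and a slope contrast. The documents give no covariate effects on change, so all of those below are assumed.

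**1. The plan's own figure.** Per arm, n = 2(1.645 + 0.842)² / 0.56² = 39.4, so 40, or 80 in total. Power at 40 per arm is 0.805 by the normal formula and 0.799 by noncentral t. For dropout, 40 / 0.7 = 57.1, so 58 per arm and 116 in total. The figure reproduces, and it contains no covariate term.

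**2. Algebra.** For woman i at time t (0 or 1), in arm g, with covariate x and random intercept u:

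y = b0 + b1·g + b2·t + b3·g·t + c·x + u + e

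T2 minus T1 = b2 + b3·g + (e2 − e1)

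Both c·x and u are gone, so b3 and its standard error do not depend on x. Adding k·x·t gives

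T2 minus T1 = b2 + b3·g + k·x + (e2 − e1)

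and b3 is now adjusted for x. In both models x is time-invariant.

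**3. Simulation, complete pairs.** These were random-intercept fits with 80 women. One data set gave a slope difference of 1.1425 (SE 0.3237) both without the covariate and with its main effect.

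Over 150 runs with a true difference of 0.56 and a deliberate arm imbalance of 0.8 SD in x, the means were:

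- no covariate: 1.212
- main effect: 1.212 (no difference in any run)
- main effect plus x-by-time: 0.583

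The implied covariate effect on change is large, about (1.212 − 0.56) / 0.8 = 0.8 per SD. The example shows the mechanism, not a likely size.

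With no built-in imbalance, as under randomization, the means were 0.544, 0.544 and 0.526. The SDs were 0.330, 0.330 and 0.287.

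**4. Simulation, 30% of T2 missing, all observed data used.** With the same built-in imbalance, mean estimates without and with the main effect were:

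- missing completely at random: 1.203 and 1.201
- missing at random: 1.196 and 1.195

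Single-trial estimates did move, by 0.070 and 0.079 on average (maximum 0.366 and 0.324), but not towards 0.56. In a separate simulation of 116 women with three covariates, the SE ratio (main effects to none) was 0.996. In three individual fits with the strong single covariate and values missing completely at random, it was 0.3649/0.3701 = 0.986, 0.3206/0.3274 = 0.979 and 0.4462/0.4622 = 0.965. The cancellation is no longer exact, but little adjustment results.

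**5. What covariate-by-time terms could gain.** The SE factor is about √(1 − R²), where R² is the share of change variance explained. Power = Φ(0.56·√20 / factor − 1.645), taking d in SDs of change. Three extra terms cost a variance factor of about (80 − 3)/(80 − 3 − 3) = 77/74 = 1.041, or 2% on the SE.

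| R² with change (assumed) | SE factor | Power | SE factor after 3-term cost | Power after cost |
|---|---|---|---|---|
| 0 | 1.000 | 0.805 | 1.020 | 0.791 |
| 0.05 | 0.975 | 0.822 | 0.994 | 0.809 |
| 0.10 | 0.949 | 0.840 | 0.968 | 0.827 |
| 0.19 | 0.900 | 0.872 | 0.918 | 0.861 |

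A simulation with covariates explaining about 19% of change variance gave an SE ratio of 0.91, in line with the last row. The detectable d at R² = 0.1 is 0.56 × 0.949 = 0.53 before the cost. The terms break even at R² of about 1 − 74/77 = 0.04.

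**The case against.** The strongest reply is that the plan does not say main effects only. Time-invariant describes a covariate's values, not its place in the model. Treatment group is itself time-invariant and is given an effect on slope, and removing terms by deviance leaves room for a fuller starting model. This stands: the point is conditional on a reading. That reading is nonetheless the natural one, since no interaction is mentioned, and under the other reading the sentence still needs completing.

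A reader might infer something stronger, that the trial will present as adjusted a slope difference that is in fact crude. The documents do not support this. They do not exclude covariate-by-time terms, and they do not call the slope difference adjusted. Nor would the test be invalid. Allocation is randomized, and a confounder that shifts both visits equally is already removed by taking the change. Only a covariate effect on change is left unhandled.

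It is also fair to say that exact cancellation needs complete pairs, whereas the plan keeps all randomized women and allows for 30% dropout. The simulations show that this alters single estimates without producing real adjustment. The size of the gain is assumed, and if the covariates do not predict change, the extra terms lose a little. Finally, the plan labels this analysis secondary, and the main hypothesis, 1a, is not touched.

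**Conclusion.** The concern holds conditionally. If confounders enter as main effects only, they leave the 1b/1c slope contrast unchanged in complete pairs. With 30% of T2 missing they leave it unchanged on average, with an SE gain between 0.4% and 3.5% in the cases examined. They would not correct a chance imbalance that affects change.

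The consequence is a modest loss of opportunity, not bias: about 5% on the SE if R-square with change is 0.1, and power of 0.84 instead of 0.80 at d = 0.56, or about 0.83 after paying for three terms. That 0.1 is borrowed from the logistic model, and the true value for change is unknown. The sample size and the stated d = 0.56 stand. The change is worth making because it is cheap and uses data already collected. It also settles the model before the data are seen.

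**What to change.** In Continuous Outcomes Analyses: Aims 1 and 2, replace the sentence on confounders with wording such as: T1 (baseline) values of the following confounders [list] enter the mixed model as main effects and with their interaction with time, so that the group-by-time term is adjusted for their effects on change; all observed visits are kept.

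The list should be fixed in advance and should say whether prenatal antibiotic use is on it. Specifying T1 settles which questionnaire supplies the value and avoids conditioning on behaviour reported after treatment has started. Keeping the mixed model is preferable to regressing the T2 count on T1 covariates, which would drop women without a T2 sample unless those values were imputed.

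If the sponsor prefers main effects only, the plan should describe the slope contrast as not adjusted for covariate effects on change.

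The cost is one sentence and about one degree of freedom per covariate term (three or more). With three terms that is about 2% on the SE if the covariates do not predict change. No new data are needed.
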